6.3. Data Management

Datasets will be created according to Clinical Data Interchange Standards Consortium (CDISC) standards. The most current or latest version of the Study Data Tabulation Model (SDTM) datasets will be used. All statistical and data analyses, SDTMs and Analysis Data Model (ADaM) datasets will be created

using (SAS[®]) software version 9.4 or later. The data specifications and reviewer's guide will also be created.

6.4. Data Presentation Conventions

6.4.1. Descriptive Statistics

Data will be summarized with descriptive statistics and/or response frequencies. For numerical data, descriptive statistics will include number of subjects with non-missing data (n), mean, standard deviation (SD), median, minimum, and maximum. For categorical data, descriptive statistics will be categorized by frequency counts and proportions (or percentages) of the number of subjects used in the analysis. The counts for the categories of 'Missing,' 'Unknown,' or 'Not applicable' will be provided as appropriate, but the percentages will not be provided.

6.4.2. Rounding

In general, the minimum and maximum will be reported to the same number of decimal places as the data. The mean, median, and confidence intervals will be rounded to one more decimal place than the data. The SD will be rounded to two more decimal places than the data. Proportions will be reported as percentages rounded to one decimal place.

Each subject's age will be truncated to a whole number (rather than rounded).

6.4.3. p-values

Not applicable.

6.4.4. Dictionaries

The Medical Dictionary for Regulatory Activities (MedDRA, version 21.0 or later version) will be used to code AEs and medical history into system organ class (SOC) and preferred term (PT) within SOC. The enhanced version of the World Health Organization Drug Dictionary (WHO-DD, WHO Drug Enhanced + Herbal B3 March 2018, or latest available version) will be used to code all medications (prior and concomitant) to anatomical therapeutic chemical (ATC) class and preferred drug names.

6.5. Baseline Definition

For all safety data, the baseline value is defined as the last non-missing measurement obtained on or before the administration of the first dose of study drug.

6.6. Derived and Transformed Data

- 6.6.1. Calculations Using Dates
- **6.6.1.1.** Baseline Age

Age for enrolled subjects will be calculated as the truncated difference (eg, fractional part ignored) between the date of the informed consent and the subject's birth date (DOB) adjusted for years (ie, AGE = int[(Visit 1 - DOB) / 365.25]).

6.6.1.2. Study Day

There is no Day 0. Study Day 1 denotes the day of the first dose and is the reference start date for all safety analyses in this study. Study days (or visit days) are defined relative to Day 1 unless otherwise specified. Days prior to Day 1 are negative and days after Day 1 are positive. That is,

Relative Day = (Date of Assessment) – (Date of First Dose of Study Drug) + 1, if assessment is on or after the date of first dose of study drug;

Relative Day = (Date of Assessment) – (Date of First Dose of Study Drug), if assessment is before the date of first dose of study drug.

6.6.1.3. Other Calculations Using Dates

Total duration of treatment will be calculated as the difference between the dates of last and first dose of study drug plus 1 day.

All other calculations of duration for enrolled subjects (eg, time since the primary diagnosis or age of first diagnosis) will be performed relative to the first dose of study drug and will follow the algorithm:

Duration = (Target Date – First Dose Date + 1).

6.6.1.4. Change from Baseline

The change from baseline will be calculated as the post-baseline visit value minus the baseline value (the value prior to or on the date of first administration of the study drug).

6.6.1.5. Visit Windows

There will be no derivation for visit windows in terms of summary assessments. Nominal visits will be used for by-visit tables. There is visit mapping rule only for monthly average scores of FABPRO-GI and Pain Questionnaire, see Section 8.3.1 for details.

6.6.1.6. Multiple Assessments

If multiple assessments including assessments at the unscheduled visit, are associated with a nominal visit post-baseline, the last assessment will be used.

6.7. Handling of Missing Data

6.7.1. Missing Start and Stop Dates for Adverse Events

For AEs, partially missing start dates will be imputed for the purpose of determining treatment emergence only.

Partially missing start dates will be imputed as follows:

For a missing day,

- If the month and year are equal to the month and year of the date of the first dose of study drug, then the date of the first dose of study drug will be used.
- Otherwise, the first day of the month will be used.

For a missing day and month,

- If the year is equal to the year of the first dose of study drug, then the date of the first dose of study drug will be used.
- Otherwise, the first day of the month and the first month of the year will be used.

If the stop date is not missing and the imputed start date is after the stop date, then the stop date will be used.

If the start date is completely missing and the stop date is on or after the date of first dose of study drug, the AE will be considered a TEAE.

If both the start date and stop date are missing, the AE will be considered a TEAE.

Missing stop dates for adverse events will not be imputed.

6.7.2. Missing Adverse Event Intensity and Relationship

If an AE is missing the intensity or relationship to study drug, the AE will be classified under the maximum intensity (ie, severe) or the maximum relationship (ie, definite), respectively.

6.7.3. Missing Start and Stop Dates for Prior and Concomitant Medications

Partially missing medication start dates will be imputed in a similar manner as described in Section 6.7.1 for imputing missing AE start dates. Missing stop dates for medications will not be imputed. If when using these rules, the imputed start date is after the stop date, then the start date will be left as missing and the medication will be considered a concomitant medication for the purpose of the analysis.

7. Demographic, Other Baseline Characteristics and Medication

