7.3. Concomitant Medications

Concomitant medications, including vaccinations, taken within 1 month before screening or at any time throughout the study must be recorded in the eCRFs, along with the reason for use, dates of administration, dosage, frequency, and route of administration.

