3.2.3. Safety Endpoints

Safety endpoints are as follows:

- incidence of treatment-emergent adverse events (TEAEs), Serious Adverse Events (SAEs), and adverse events (AEs) leading to discontinuation of study drug
- changes in clinical laboratory test results from baseline over time
- changes in vital signs from baseline over time
- changes in physical examination findings from baseline over time
- changes in body weight and height from baseline over time
- changes in 12-lead electrocardiogram (ECG) results from baseline over time
- changes in ECHO parameters from baseline to Month 12/ET
- change in Tanner stage from baseline to Month 12/ET
- use of concomitant medications

[figure not shown]
4. Study Design

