7.4. Prior and Concomitant Medications

Medications will be classified as prior (started prior to the first dose of study treatment) and concomitant (continued past or started on or after the first dose of study treatment).

All prior and concomitant medications will be classified using the ATC classification coded terms and preferred drug names from the WHO-DD.

Summaries of prior and concomitant medications will be presented separately in tabular form using the level 4 ATC term as an upper classification level and the preferred drug name as a lower classification level. All medications will be summarized and sorted alphabetically by level 4 ATC term and preferred drug name within a given level 4 ATC term. The summary will consist of the frequency and percentage of safety subjects who used the medication at least once.

For each subject, the medication will be counted only once within a level 4 ATC term and only once under a given preferred drug name. A subject may appear more than once if he/she has more than one concomitant medication coded under different ATC terms or preferred drug names; however, the subject will be counted only once in the overall category.

A by-subject listing with coded terms will also be provided along with calculated study days.

Prior ERT will be summarized by preferred drug name for the safety population.

8. Efficacy

Observed values and changes from baseline for each efficacy endpoint in Section 3.2.1 will be summarized with descriptive statistics at each scheduled time point based on the ITT population. Mean plots including standard error bars at each visit for the numerical observed values and changes from baseline of the indicated laboratory assessments, ECHO results and subject questionnaires will be provided by sex (male, female), ERT status (ERT naïve, ERT experienced), and overall, if feasible.

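### SAP 6.7.3 labels a medication concomitant when its partial start was imputed to first dose but it is known to have stopped earlier, contrary to SAP 7.4 and the stop-date rule in 6.7.1

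*SAP*

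**What the plan says.** SAP 7.4 defines the two classes. "Medications will be classified as prior (started prior to the first dose of study treatment") is one half of the definition; the other is "concomitant (continued past or started on or after the first dose of study treatment"). A drug that began before first dose and ran on can belong to both. A drug that ended before first dose can only be prior. The two classes are tabulated separately, as percentages of safety subjects.

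SAP 6.7.3 deals with incomplete dates: "Partially missing medication start dates will be imputed in a similar manner as described in Section 6.7.1". Stop dates are not imputed. Its last sentence covers an imputed start that falls after the stop: "then the start date will be left as missing and the medication will be considered a concomitant medication for the purpose of the analysis".

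SAP 6.7.1, the section it refers to, sets a partial start in the month of first dose (day missing) to the first-dose date. For a start known only by year, the rule begins "If the year is equal to the year of the first dose of study drug, then the date of the first dose", and that date is imputed. All other partial starts go to the first day of the month or to 1 January. For a clash with the stop date, 6.7.1 says: "If the stop date is not missing and the imputed start date is after the stop date, then the stop date will be used".

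SAP 3.2.3 lists "use of concomitant medications" among the safety endpoints. Protocol 7.3 requires medications to be recorded if "taken within 1 month before screening or at any time throughout the study must be recorded in the eCRFs", so drugs that ended before first dose will be in the database.

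**The concern.** A default to concomitant is reasonable when it is unclear whether a drug overlapped treatment. The 6.7.3 fallback does not address that case. It needs a known stop date, and for consistent dates that stop precedes first dose, so no overlap is possible. The label it assigns is one the SAP's own definition excludes.

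The section also says it works like 6.7.1, then prescribes a different outcome for the same trigger. A programmer has two readings:

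- **Literal:** the 6.7.3 sentence replaces the 6.7.1 stop-date clause, and drugs that ended before first dose enter the concomitant table.
- **Imported:** the 6.7.1 clause is applied first. The imputed start can then never exceed the stop, and the last sentence of 6.7.3 has no effect.

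On the literal reading the concomitant table is overstated. The prior table may be understated, because the start date has been set back to missing. With about 20 subjects planned (Protocol 8.1), one misplaced subject moves a table row by about 1/20 = 5 percentage points.

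**Working it through.** The plan gives no figure to reproduce. The check is logical, with an enumeration to confirm it.

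**Step 1: when can the imputed start exceed the stop?** Under 6.7.1 the imputed start takes one of two values.

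- *Earliest date the partial allows* (first of the month, or 1 January). The true start is on or after it and the stop is on or after the true start, so it cannot exceed a consistent stop.
- *First-dose date.* It exceeds the stop exactly when the stop is before first dose.

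For consistent records the fallback therefore fires only for drugs that stopped before first dose.

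**Step 2: compare the labels.** First dose is assumed to be 15 June 2019 and the stop is 20 May 2019, which is 11 + 15 = 26 days earlier and inside the Protocol 7.3 recording window.

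| Recorded start | Imputed start | Fallback fires? | Label under literal 6.7.3 | Label under SAP 7.4 |
|---|---|---|---|---|
| 2019 | 15 Jun 2019 | yes | concomitant | prior only |
| May 2019 | 1 May 2019 | no | prior | prior only |
| 2018 | 1 Jan 2018 | no | prior | prior only |

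In the first row the 6.7.1 clause would give a start of 20 May 2019, hence prior. A month-only case also exists: with first dose 15 July 2019, start July 2019 and stop 9 July 2019, the start is imputed to 15 July and the fallback fires.

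**Step 3: enumerate.** Inputs (assumed): first dose 15 June 2019; every pair with true start on or before stop, from 365 days before to 360 days after first dose; each pair taken once with the day missing and once with day and month missing.

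- Days in the window: 365 + 1 + 360 = 726. Combinations: 2 × (726 × 727 / 2) = 527,802.
- Year-only starts that fire: 165 days from 1 January to 14 June, 165 × 166 / 2 = 13,695.
- Month-only starts that fire: 14 days from 1 to 14 June, 14 × 15 / 2 = 105.
- Total: 13,695 + 105 = 13,800, all with the stop before first dose.
- Combinations with the stop before first dose: 2 × (365 × 366 / 2) = 133,590. Share reached: 13,800 / 133,590 = 10.3%.
- With the 6.7.1 stop-date clause applied first: 0 firings.

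**Step 4: vary the assumed first-dose date.**

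- 15 January: 105 + 105 = 210 firings, 210 / 133,590 = 0.2%.
- 15 December: 348 × 349 / 2 = 60,726, plus 105 = 60,831 firings, or 45.5%.

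The range is wide because year-only starts are exposed only from 1 January of the first-dose year. A coarser grid in 3-day steps (64,320 combinations per date) gave 0 firings for 1 January, 372 for 20 March, 2,155 for 15 July and 7,436 for 31 December. Every one had stopped before first dose, and none was mislabelled once the stop date was used as the start.

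**The case against.** The strongest reply has four parts.

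1. **6.7.1 is written for adverse events.** Section 6.7.3 says similar, not identical, and states its own outcome, so a difference between the two is not by itself an error. This has force. The firm conflict is with the definition in 7.4; the mismatch with 6.7.1 shows that the text is ambiguous and that the SAP already contains a workable rule.
2. **The impact is small.** The study is uncontrolled, p-values are not applicable (SAP 6.4.3), and no efficacy, pharmacokinetic, pharmacodynamic or adverse event summary is described as using this label. The by-subject listing would still show the stop date, and imputed values are flagged in listings (SAP 6.1). All of this stands and limits the weight of the point.
3. **The enumeration is not a frequency.** It weights every date pair equally, and its percentage depends on the assumed first-dose date. This also stands: it shows where the rule can fire, not how often it will.
4. **Prior enzyme replacement therapy adds little.** It has its own summary (SAP 7.4) and baseline variable (SAP 7.2), and neither is said to depend on the label. That is fair. It is a corner case, reached essentially only when the start is known by year alone and that year is the first-dose year. The result would still be awkward: a therapy that Protocol 7.4 prohibits during the study would appear as concomitant.

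None of these makes the label right for a drug known to have ended before first dose.

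**Conclusion.** The concern holds. On the literal reading, every date-consistent record that reaches the 6.7.3 fallback receives a label that SAP 7.4 rules out. On the other reading, the sentence is dead text at odds with the section it cites.

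The conclusion assumes a complete stop date that is consistent with the partial start. Given a known stop date, drugs with a full start date, or with a partial start in an earlier month or year than first dose, are classified correctly. Records with contradictory dates are outside the claim. For example, with first dose 15 June 2019, start September 2019 and stop 20 August 2019, the fallback also fires, and there concomitant is the right label.

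The consequence is limited to descriptive medication tables, and the number of affected trial records cannot be derived from the documents. It should still be corrected, because it is a wrong rule in the derivation of a listed safety endpoint.

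**What to change.** Replace the last sentence of SAP 6.7.3 with: *If the imputed start date falls after the stop date, the start date is set to the stop date; a medication whose stop date is before the first dose of study drug is prior only.*

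This wording also gives the right answer for the contradictory record above: the start becomes 20 August 2019, hence concomitant. A default to concomitant should be confined to drugs whose stop date is missing or cannot be placed before first dose. Section 6.7.3 has no such rule at present, so if one is wanted it must be written out as a separate sentence.

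The cost is one SAP sentence and a small programming change. No data collection is affected.

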7.1. Subject Disposition and Withdrawals

Frequency counts and percentages of all subjects who are enrolled but do not take study drug, and subjects who are enrolled and complete the study drug/study or discontinue study drug/study early will be presented. All subjects who discontinue from the study will be identified, and their reason for discontinuation in the study will be reported. The denominators for the percentage calculations will be the number of subjects in ITT population.

The following frequencies (number and percentage) will be displayed:

- Subjects in the ITT population
- Subjects in the safety population
- Subjects in the PK population
- Subjects who completed the study
- Subjects who discontinued early overall and by reason

In addition, the number of screened subjects and screen failures will be provided.

A listing of all study subjects, whether they discontinued the study or not, and the reasons for study discontinuations will be provided for the ITT population.

7.2. Demographic and Other Baseline Characteristics

Demographic and baseline data will be summarized by means of descriptive statistics: continuous variables as mean, SD, median, minimum, and maximum, and categorical variables as frequencies and percentages, based on the ITT population. Demographic data will include age (continuous and categorical), gender, race, ethnicity, reproductive potential, height, body weight, and body mass index (BMI). Baseline characteristics will include number of years since diagnosis of Fabry disease, previous use of ERT, and previous and current use of angiotensin-converting enzyme inhibitors, renin inhibitors, and angiotensin receptor blockers. The following calculations will be utilized:

- Age = (informed consent date date of birth + 1) / 365.25 and truncated to complete years
- Weight (in kg) = weight (in pounds) *0.4536
- Height (in cm) = height (in inches) * 2.54
- BMI (kg/m^2) = weight(kg)/[(height(cm)/100)²], where m = meters
- Number of years since diagnosis of Fabry disease = (informed consent date date of diagnosis of Fabry disease + 1) / 365.25 and rounded to 1 decimal; for any missing days or months, years will be used for the calculation: Number of years since diagnosis of Fabry disease = (year of informed consent date year of date of diagnosis of Fabry disease; for missing years, number of years will be missing.
- A month will be defined as 30 days.
- ERT status is defined as ERT naïve and ERT experienced.

All demographic and baseline characteristic data will also be listed, including the protocol version (captured in eCRF) under which the subject was screened and the date of informed consent.

7.3. Medical History

A summary table of the number and percentage of subjects for medical history by SOC and PT will be produced for subjects in the safety population. Medical history will be sorted alphabetically by SOC and PT within the same SOC using the MedDRA coding dictionary, version 21.0 or later version. For the summary tables, a subject may appear more than once if he/she has more than one medical history coded under different SOC or PT categories. However, the subject will be counted only once in the overall category. A by-subject listing with coded SOC and PT along with verbatim Case Report Form (CRF) term will also be provided.

7.4. Prior and Concomitant Medications

Medications will be classified as prior (started prior to the first dose of study treatment) and concomitant (continued past or started on or after the first dose of study treatment).

All prior and concomitant medications will be classified using the ATC classification coded terms and preferred drug names from the WHO-DD.

Summaries of prior and concomitant medications will be presented separately in tabular form using the level 4 ATC term as an upper classification level and the preferred drug name as a lower classification level. All medications will be summarized and sorted alphabetically by level 4 ATC term and preferred drug name within a given level 4 ATC term. The summary will consist of the frequency and percentage of safety subjects who used the medication at least once.

For each subject, the medication will be counted only once within a level 4 ATC term and only once under a given preferred drug name. A subject may appear more than once if he/she has more than one concomitant medication coded under different ATC terms or preferred drug names; however, the subject will be counted only once in the overall category.

A by-subject listing with coded terms will also be provided along with calculated study days.

Prior ERT will be summarized by preferred drug name for the safety population.

8. Efficacy

Observed values and changes from baseline for each efficacy endpoint in Section 3.2.1 will be summarized with descriptive statistics at each scheduled time point based on the ITT population. Mean plots including standard error bars at each visit for the numerical observed values and changes from baseline of the indicated laboratory assessments, ECHO results and subject questionnaires will be provided by sex (male, female), ERT status (ERT naïve, ERT experienced), and overall, if feasible.

8.1. Laboratory Assessments

Efficacy analyses will include summaries of observed and change from baseline values for the eGFR, urine protein and albumin for scheduled visits, indicated in Section 4.6. Scheduled visits will only be included for by-visit summary.

Annualized rate of change from baseline of eGFR will be included in the summary table. Annualized rate of change from baseline of eGFR is defined as change from baseline to last visit divided by the duration from baseline to the last visit (Last assessment date – First dose date +1) and multiplied by 365.25.

A by-subject listing will be presented for each laboratory test.

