8.3. Withdrawal Criteria

Subjects may discontinue study drug, withdraw from the study, or be withdrawn from the study for any reason including, but not limited to, the following reasons:

- at their own request or at the request of their parent or legally-authorized representative
- if, in the investigator's opinion, continuation in the study would be detrimental to the subject's well-being
- occurrence of an intolerable AE as determined by the investigator, subject, and/or parent or legally-authorized representative
- inability to tolerate or comply with PK blood sampling procedures
- failure of the subject to comply with the study visit schedule
- persistent noncompliance, at the discretion of the investigator
- pregnancy
- inability to contact subject (ie, subject is lost to follow-up)
- sponsor request

The reason for and date of discontinuation or withdrawal must be recorded in the eCRF and in source documents. All subjects who discontinue study treatment will be encouraged to complete an early termination (ET) visit and follow-up safety assessments.

The investigator must make every effort to contact subjects who are lost to follow-up to schedule end-of-study assessments. Attempts to contact subjects who are lost to follow-up (eg, times and dates of attempted telephone contact, documentation of a registered letter) must be recorded in the subject's source document.

If a subject wishes to discontinue treatment, the investigator must determine the extent that a subject may be willing to continue participation in the study, as follows:

- the parent or legally-authorized representative and/or subject wants to discontinue study drug, but agrees to the follow-up procedures
- the parent or legally-authorized representative and/or subject wants to discontinue study drug and all follow-up procedures
- the parent or legally-authorized representative and/or subject wants to revoke consent/assent to collect and use further data

Note: In the United States, the authorization to use and disclose data for research can only be revoked in writing by the subject, or parent or legally-authorized representative of minor subjects.

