Window (days)				±3	±3	±3	±3	±3	±6	±6	±6	±6	±6	±6	± 6	+6
Visit Number	1	2	3	4	5	6	7	8	9	10	11	12	13	14	15	16
Complete physical examination	X	X				X			Х						Х	
Brief physical examination			X	X								Х				
Adverse events		X	X	X	Х	X	X	Х	Х	Х	X	Х	Х	Х	Х	Х
Vital signs (BP, HR, RR, Temp)	X	Х	Х	X		X			X			Х			Х	
Body weight	X	X	X	X		X			Х			Х			Х	
Height	X	X		X		X			Х			Х			Х	
Tanner Staging		X							Х						Х	
12-Lead ECG	X	X							Х						Х	
Chemistry (including eGFR using Schwartz formula)	X	Х				X			Х						Х	
Hematology		Х							Х						Х	
Plasma lyso-Gb ₃ and analogs		Х				X			X						Х	
Exploratory PD biomarkers		Х							X						Х	
PK blood samples			X ^d						X						Х	

Table 3:Schedule of Assessments (Continued)

13 June 2019 Confidential

	Screening	ı	Treatment Period							Treatment Period						
		S	tage 1							Stage 2						
Assessments	Day -30 to -14	Baseline ^b Day 1	Day 15-30	Month 1	Month 2 (TC)	Month 3	Month 4 (TC)	Month 5 (TC)	Month 6	Month 7 (TC)	Month 8 (TC)	Month 9	Month 10 (TC)	Month 11 (TC)	Month 12/ET	30-Day Safety ^c
Window (days)	_			±3	±3	±3	±3	±3	±6	±6	± 6	±6	±6	±6	± 6	+6
Visit Number	1	2	3	4	5	6	7	8	9	10	11	12	13	14	15	16
Urinalysis (urine protein and albumin or microalbumin levels)	X	X		Х		Х			Х						Х	
Urine pregnancy test or date of LMP (as applicable) ^e	X	Х		Х	Х	X	Х	Х	Х	X	Х	Х	X	Х	Х	
Echocardiogram (LVMi and additional parameters)	Х	Х							X						X	
Study treatment supply/ Resupply/Return		X		Х		Х			Х			Х			Х	

Table 3:Schedule of Assessments (Continued)

Abbreviations: BP = blood pressure; ECG = electrocardiogram; eGFR = estimated glomerular filtration rate; ET = early termination; FABPRO-GI = Fabry Disease Patient-Reported Outcome-Gastrointestinal; FPHPQ = Fabry-Specific Pediatric Health and Pain Questionnaire; $GLA = gene encoding \alpha$ -galactosidase A; HR = heart rate; LMP = last menstrual period; LVMi = left ventricular mass index; lyso-Gb₃ = globotriaosylsphingosine; PD = pharmacodynamic; PedsQL = Pediatric Quality of Life Inventory; PGI-C = Patient Global Impression of Change; PK = pharmacokinetic; RR = respiration rate; TC = telephone call;

Temp = body temperature

^a For subjects without a documented *GLA* variant, screening procedures will be suspended until such time that a confirmed, amenable variant is determined.

^b All baseline assessments must be completed BEFORE the first dose of migalastat is administered.

^c Only for subjects who do not enroll in a long-term extension study

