9.1.4. Unscheduled Visits

Unscheduled visits for medical reasons such as evaluation of AEs and/or repeat laboratory tests can be performed at any time at the investigator's discretion. The date and reason for the visit, in addition to all information collected during the visit, should be captured in source documents and on the appropriate eCRFs.

Follow-up visits triggered by subjects' weight monitoring also are considered unscheduled visits for data management purposes.

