9.1.5. Early Termination Visit

Subjects who are withdrawn from the study should complete Month 12/ET procedures as soon as possible. If early termination coincides with a scheduled visit (ie, Visit 4, 6, or 10), all procedures outlined for the ET visit should be performed.

9.1.6. **30-day Safety Follow-up Visit**

All subjects who do not enroll in a long-term extension study, including subjects who discontinue study drug or withdraw from the study, should complete a 30-day safety follow-up visit, to be scheduled at least 30 days after the last dose of study drug.

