5.2. Intent-to-Treat Population

The intent-to-treat (ITT) population will include all enrolled subjects. All efficacy analyses will be performed using the ITT population.

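### The annualized eGFR rate in SAP 8.1 has no minimum follow-up or weighting, so one early leaver can distort its mean and SD

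*SAP*

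**What the plan says.** SAP 3.2.1 lists the annualized rate of eGFR change among the efficacy endpoints; Protocol 11.1.4 does not. SAP 8.1 is therefore its only definition: "Annualized rate of change from baseline of eGFR is defined as change from baseline to last visit divided by the duration from baseline". The duration is the last assessment date minus the first dose date plus 1, and the result is multiplied by 365.25.

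On who is included, SAP 5.2 says "All efficacy analyses will be performed using the ITT population". The introduction to SAP section 8 says efficacy endpoints "will be summarized with descriptive statistics at each scheduled time point based on the ITT population". On the statistics, SAP 6.4.1 says: "For numerical data, descriptive statistics will include number of subjects with non-missing data (n), mean, standard deviation (SD), median, minimum, and maximum". None of these is weighted.

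On how an early value can arise, Protocol 9.1.5 says "Subjects who are withdrawn from the study should complete Month 12/ET procedures as soon as possible", and it names Visit 4 (Month 1) and Visit 6 (Month 3) among the scheduled visits that early termination may coincide with. The row "Chemistry (including eGFR using Schwartz formula" in Protocol Table 3 is marked at screening, baseline, Month 3, Month 6 and Month 12/ET, but not at Month 1. Protocol 9.1.4 adds: "Unscheduled visits for medical reasons such as evaluation of AEs and/or repeat laboratory tests can be performed at any time". SAP 8.1 limits only its by-visit summary to scheduled visits, so it is not stated whether an unscheduled eGFR can be the last one for the rate.

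**The concern.** The multiplier is the inverse of follow-up time, so the shortest and least informative records are inflated most. An unweighted mean then gives them the same weight as a full year of follow-up. The rule also uses only two eGFR values per subject, although a completer also has Month 3 and Month 6 values.

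Elsewhere the SAP does guard against thin data. A monthly diary average is set to missing after more than 6 missing days (8.3.1), and a PedsQL score is withheld when more than half its items are missing (8.3.4). The eGFR rate, where thin data are multiplied, has no such rule.

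At stake is how readable the mean and SD of one efficacy measure are in a trial of about 20 subjects. Ordinary variation in a single early leaver could look like a shift in renal course.

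**Working it through.** The plan states no figure for this rate, so there is none to reproduce. The SAP formula was applied directly.

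**Inputs from the documents.** The month is 30 days (Protocol 11.3.2) and Day 1 is the first dose (SAP 6.6.1.2). Months 1, 3, 6 and 12 therefore fall at about Days 31, 91, 181 and 361. About 20 subjects are planned (Protocol 8.1).

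**Assumptions, not in the documents.** One leaver among 20; a chance eGFR change of 10 mL/min/1.73 m² (range 5 to 15); measurement SD 10; between-subject SD of true slope 10 per year; intercept SD 20.

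**Step 1: multiplier = 365.25 / D**, where D is the study day of the last eGFR. **Step 2: shift in the mean of 20 = change × multiplier / 20.**

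| Last eGFR | Multiplier | Shift for a change of 10 (5 to 15), per year |
|---|---|---|
| Day 31 | 365.25/31 = 11.78 | 5.89 (2.95 to 8.84) |
| Day 91 | 365.25/91 = 4.01 | 2.01 (1.00 to 3.01) |
| Day 181 | 365.25/181 = 2.02 | 1.01 (0.50 to 1.51) |
| Day 361 | 365.25/361 = 1.01 | 0.51 (0.25 to 0.76) |

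Protocol 11.3.2 generally summarizes by sex. In a sex group of 10 (assumed) each shift doubles, to 11.8 for Day 31 and 4.0 for Day 91.

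**Step 3: precision of the mean rate.** The variance of one subject's rate is (10 × (D−1)/D)² + 2 × 10² × (365.25/D)².
- Completer: 99 + 205 = 304.
- Day 91 leaver: 98 + 3,222 = 3,320.
- Day 31 leaver: 94 + 27,764 = 27,858.

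Standard error of the mean of 20:
- All complete: √(20 × 304)/20 = 3.90.
- One Day 91 leaver: √(19 × 304 + 3,320)/20 = 4.77.
- One Day 31 leaver: √(19 × 304 + 27,858)/20 = 9.17.

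**Step 4: reported SD and median.** In 100,000 simulated samples of 20, the typical reported SD is 17.1 with no leaver. It is about 20 with a Day 91 leaver (about 1.15-fold) and about 30 with a Day 31 leaver (about 1.8-fold). Over measurement SD 5 to 15 and slope SD 0 to 15, the ratios are 1.06 to 1.20 and 1.30 to 2.05. The sampling error of the median rises only about 3% to 5%.

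**Step 5: the alternative.** A linear mixed model with subject intercept and slope was evaluated by generalized least squares. It used values at 0, 90, 180 and 360 days for 19 completers and two values for the leaver. The table shows how far the mean slope moves per year when the leaver's change is 10 by chance.

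| Leaver | Error all in last value | Error all in baseline | Two-point rule |
|---|---|---|---|
| Day 31 | 0.02 | 0.10 | 5.89 |
| Day 91 | 0.16 | 0.21 | 2.01 |

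The standard error of the mean slope is 3.80 with no leaver, 3.89 with a Day 31 leaver and 3.88 with a Day 91 leaver.

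**The case against.** The strongest reply is that little depends on this row. SAP 6.4.3 marks p-values as not applicable, the sample size rests on pharmacokinetics, and efficacy is a secondary objective of Stage 2. The plan also reports the unannualized change by visit, the median, minimum and maximum, and by-subject listings. An extreme rate would show up as the minimum or maximum. All of that stands, and it is why the point is minor.

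The second reply is that the worst case is rare. Chemistry is not scheduled at Month 1, Protocol 8.3 says only that subjects who stop treatment "will be encouraged to complete an early termination (ET) visit", and no dropout rate is given. That stands too. The protocol synopsis does list a Month 1 eGFR change among the endpoints, so a reader might infer that Month 1 values are routine. Table 3, Protocol 11.1.4 and the SAP do not support that.

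A reader might also infer that every enrolled subject receives a rate. A subject who was never dosed has no first dose date and so no rate, and a subject without a baseline or post-baseline eGFR has none either.

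The third reply is that a mixed model is a matter of preference in a descriptive plan. It is a choice of method, but no other passage weights or limits the rate, and the two-point mean handles short follow-up poorly.

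**Conclusion.** The point holds as a minor, cheap improvement. The multipliers of 1.01, 4.0 and 11.8 follow from the documents alone. The shifts of 2.0 (Month 3) and 5.9 (Month 1) per year, against 0.5 in a completer, rest on one assumed leaver among 20 and an assumed chance change of 10. The SD and mixed-model figures also rest on assumed variance components. At Month 3 the effect is modest; it is large only with an early-termination or unscheduled eGFR near Month 1.

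It would be tempting to conclude that the trial's renal findings are unreliable. The documents do not support that: no test uses the rate, and the by-visit eGFR changes are not annualized. Nor is the mixed model immune to an early leaver. Its shift is small, but it depends on whether the error lies in the last or the baseline value.

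**What to change.** Keep the planned two-point summary. Add to SAP 8.1, as a supporting row, the mean eGFR slope from a linear mixed model with subject intercept and slope. Use the SAP's own baseline (the last value on or before first dose, SAP 6.5 and 6.6.1.4) and the Month 3, 6, 12 and early-termination values. State whether unscheduled values count, and use the same set of values for the model and the two-point rate.

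Optionally, list separately the raw change and follow-up time of subjects whose last eGFR precedes the Month 6 window. That window opens at Day 174 or 175 (Day 180 or 181 minus 6), where the multiplier is 2.1. A two-point summary restricted to later follow-up could be shown, but as supporting only, because it selects on follow-up. If the one leaver's true slope differs from the others' by 10 to 20 per year (assumed), leaving that subject out shifts the result by 10/20 = 0.5 to 20/20 = 1.0 per year.

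The cost is two or three sentences and one or two table rows, with no new data. The downsides are a missing-at-random assumption and one model-based result beside descriptive statistics.
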